7. PLANNED ANALYSIS

Unless otherwise specified, all analyses described in this section will be done on the Treated Set. The labelling and display format of statistical parameters will follow BI standards ([10](#)). For End-Of-Text (EoT) tables, the set of summary statistics is: N / Mean / SD / Min / Median / Max.

In descriptive statistics tables, mean, SD and median will be rounded to one additional digit than the raw individual value. In case some endpoints show some extreme data outside the expected range, quartiles and percentiles will be presented additionally.

Tabulations of frequencies for categorical data will include all possible categories and will display the number of observations in a category as well as the percentage (%) relative to the respective treatment group (unless otherwise specified, all patient in the respective subject set whether they have non-missing values or not). The precision for percentages should be one decimal point. The category missing will be displayed only if there are actually missing values.

Unless otherwise specified, all analyses will be provided by randomized treatment group (placebo or nintedanib) and overall (total).

[figure not shown]
For efficacy and safety end point analyses by time point, as well as for the safety analyses of Part A, patients switching during Part A to Part B will be censored at the time point of the switch and for the safety analyses of Part A (due to the definition of the double-blind period). Patients who started directly in Part B will be analyzed as a separate cohort, in addition to those randomized to nintedanib and those randomized to placebo.

[figure not shown]
All analyses performed after DBL1 will be repeated after DBL2 to include newly emerging data.

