¹³PK samples will be taken before drug administration at the clinic and at 6 timepoints post-dose (see [Flow Chart for PK blood sampling](#) for details). In exceptional cases, where extensive PK sampling is not possible and only in paediatric patients with an age < 12 years, a sparse sampling approach might be applied with a minimum blood sampling before (PTM of -0:05), 1 h (+/- 15 min) and 3 h (+/- 15 min) after nintedanib administration. Date and exact clock time of drug administration and blood sampling must be recorded in the eCRF. The patient and parent(s)/legal guardian will be provided (Visit 2 and Visit 6) with a PK diary card to support the record of the exact clock time of medication intake on the three days preceding PK sampling. At the beginning of the PK sampling visit (Visit 3 and Visit 7) the site personnel will check the PK diary card and confirm that the trial medication has been taken in the three days preceding the visit. If this is not confirmed, the visit will be rescheduled.

¹⁴At this visit drug accountability is to be completed only in case of dose reduction / increase.

¹⁵The PedsQL™ questionnaire should always be administered in a quiet place prior to any other visit procedure.

¹⁶Bone imaging (Magnetic Resonance Imaging (MRI) examination; if MRI cannot be performed, x-ray assessment) will be conducted in all patients who qualified for randomisation at baseline. Imaging follow-up will be conducted only in patients with open physes at 12 weeks, 24 weeks, 36 weeks, 52 weeks and every 24 weeks thereafter until the end of the study or closure of the physes. At EoT the MRI/x-ray should not be repeated if the last MRI/x-ray was conducted within 12 weeks in the first year, 24 weeks thereafter.

Dental examination (clinical) will be conducted in all patients who qualified for randomisation at baseline. Follow-up will be conducted in all patients at 12 weeks, 24 weeks, 36 weeks, 52 weeks and every 24 weeks thereafter until the end of the study. At EoT the dental examination will not be repeated if the last examination was conducted within 12 weeks.

Dental imaging (panoramic x-ray) will be conducted in all patients who qualified for randomisation at baseline. Follow-up will be conducted in all patients at 24 weeks, 52 weeks and every 48 weeks thereafter until the end of the study. At EoT the dental imaging should not be repeated if the last dental imaging was conducted within 24 weeks.

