5.2.5 Assessment of pathological findings of epiphyseal growth plate

MRI assessments of the distal femur and proximal tibia will be conducted as primary bone imaging methodology to assess the potential risk of skeletal toxicity of nintedanib in the growing population. In each patient the same side should be imaged at each assessment. In situations in which MRI cannot be performed, especially if sedation is required, x-rays of the distal femur and proximal tibia (AP knee radiograph) will be conducted as secondary methodology.

MRIs/x-rays of growth plates will be conducted in all patients who qualified for randomisation at baseline. Imaging follow-up will be conducted only in patients with open physes, at 3 months, 6 months, 9 months, 12 months after start of trial medication, and every 6 months thereafter until end of the study or closure of physes.

The same acquisition protocol specifications should be used for all MRIs/x-rays of growth plates. Details will be provided in the image acquisition guideline for bone safety monitoring available in the ISF. Whenever possible, scans should be completed on the same scanner and by the same radiologist at each site. Scans will be transferred for central review and stored at the sponsor facilities or by an external vendor.

MRI/x-ray assessments will be evaluated in a centralised manner by a blinded external expert in radiology. In addition, all MRI/x-ray assessments and height measurements (see [Section 5.2.1.2](#)) will be periodically reported to the Safety Monitoring Committee.

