5.2.2 Secondary endpoint(s)

Endpoints will be used as defined in the CTP Section 2.1.3. Additional specifications are given below.

5.2.2.1 N (%) of patients with treatment-emergent pathological findings of epiphyseal growth plate on imaging at week 24, and week 52

Pathological findings which were already present at baseline imaging will NOT be considered treatment-emergent in this analysis, in spite identified after start of treatment, in order to be able to separate:

- findings that were identified on the follow-up MRI/x-ray and were already present on the baseline MRI/x-ray (i.e. not treatment-emergent)
- findings that were identified on the follow-up MRI/x-ray and were NOT already present on the baseline MRI/x-ray (i.e. treatment-emergent).

There are two possible kinds of predefined pathological findings for the growth plate recorded in the Safety Read Results:

- Pathological Findings at the Distal Femur
- Pathological Findings at the Proximal Tibia

A pathological finding of epiphyseal growth plate is defined as a pathological finding at the distal femur or the proximal tibia.

More precisely,

- Thickening of the epiphyseal growth plates
- Swelling of articular cartilage

will be captured as pathological findings.

Whereas,

- Narrowing of the lucent growth plate margin compared to the baseline time point (at post-baseline time points only)
- Metaphyseal lines
- Other findings

will only be captured as pathological findings if judged pathological.

Frequencies will be reported in a cumulative way over 24 and 52 weeks, respectively.

5.2.2.2 N (%) of patients with treatment-emergent pathological findings on dental examination or imaging at week 24, and week 52

Pathological findings which were already present at baseline imaging/examination will NOT be considered treatment-emergent in this analysis, in spite identified after start of treatment, in order to be able to separate:

- findings that were identified on the follow-up panoramic x-ray and were already present on the baseline panoramic x-ray (i.e. not treatment-emergent)
- findings that were identified on the follow-up panoramic x-ray and were NOT already present on the baseline panoramic x-ray (i.e. treatment-emergent).

For the dental examination, pathological findings will be identified through the dental examination eCRF pages where the question ‘Is this a new abnormal finding’ is answered with ‘Yes’ and thus, an AE page is filled in.

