6.3 SUBJECT SETS ANALYZED

The following analysis sets are defined for this trial:

- **Screened set (SCS):**
This patient set includes all patients having signed informed consent.
- **Randomised set: (RS)**
This patient set includes all randomised patients, whether treated or not.
- **Treated Set (TS):**
The Treated Set (TS) consists of patients who are randomized to a treatment group and receive at least one dose of study medication.
- **Pharmacokinetic parameter analysis set (PKS):**
This set includes all patients in the treated set (TS) who provide at least one PK endpoint that was not excluded due to a protocol deviation relevant to the evaluation of PK or due to PK non-evaluability (as specified in the CTP Sec. 7.2.1.). Thus, a patient will be included in the PKS, even if he/she contributes only one PK parameter value for one period to the statistical assessment. Descriptive and model based analyses of PK parameters will be based on the PKS.

Analyses for PK endpoints will be based on the PKS. All other analyses will be based on the TS except for disposition.

Table 6.3: 1 Patient sets analyzed

Class of endpoint	Patient set		
	SCS	TS	PKS
Primary endpoint PK			X
Primary endpoint Safety		X	
Secondary endpoints		X	
Further endpoints Efficacy		X	
Further endpoints PK			X
Safety endpoints		X	
Demographic/baseline characteristics		X	
Disposition	X		

Note that the number of patients with available data for an endpoint may differ. For details, see [Section 6.6](#)

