6.6.2.3 Categorical endpoints

In the analyses of the binary endpoints, multiple imputation will be used to handle missing data at week 24. For week 52 and later, data will not be imputed and only observed values will be used.

The following process describes the multiple imputation for spirometry data (FVC % pred. and SpO₂) and for PedsQL™ point data. Therefore, the words “data” and “value” stand for the data and value of the respective kind of data to be imputed.

In a first step non-monotone missing data will be imputed $m = 100$ times using MCMC (Markov Chain Monte Carlo) to generate m data sets of longitudinal data with monotone missingness pattern. Such a missingness pattern is the pre-requisite for subsequently applying sequential imputation and means that once a patient has a missing value at a particular time point, the corresponding values at all subsequent time points also have missing values. The seemingly large number of imputations ($m=100$) is chosen to minimize the standard error of those estimates that are produced to fill the missing values. The seed number will be set to

1199337. For this step all available data of the respective kind will be used, restricted to one value per patient and analysis time window according to selection process described in [Section 6.7](#) below.

In a second step a regression model including baseline value and measurements at all post-baseline analysis visits scheduled (see [Table 6.7: 1](#) and [Table 6.7: 6](#), respectively) by treatment, will be used to complete the imputation in each dataset.

For each imputed complete dataset, the proportion of non-responders (and the corresponding standard error) will be used for the analysis. The results will be pooled following the standard multiple imputation procedure ([9](#)).

Patients with missing baseline value will be excluded from the analysis.

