7.5.2.3 Categorical endpoints, safety and tolerability endpoints

Only descriptive analyses in the form of frequency tables will be performed.

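### The growth-plate percentage is, by the visible SAP default, taken over all treated patients, including those with closed physes who get no follow-up bone image; the week-52 base is not settled

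*SAP*

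**What the plan says.** **Who is imaged.** Protocol Flow Chart footnote 16 and section 5.2.5 require a baseline MRI or x-ray in everyone who qualifies for randomisation. After that, "Imaging follow-up will be conducted only in patients with open physes", until the end of the study or closure.

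**What counts as a case.** SAP 5.2.2.1 requires a finding on a follow-up image that was absent from the baseline image. It adds: "Frequencies will be reported in a cumulative way over 24 and 52 weeks, respectively".

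**The base.** SAP 6.3 states: "All other analyses will be based on the TS except for disposition"; its table also marks the TS for secondary endpoints. SAP 7 sets the percentage base as "all patient in the respective subject set whether they have non-missing values or not", subject to other specification, and displays a category for missing values when there are any. SAP 7.5.2.3 adds only: "Only descriptive analyses in the form of frequency tables will be performed". None of the visible text gives a separate base for this endpoint.

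**Missing data.** SAP 6.6.2.3 says: "In the analyses of the binary endpoints, multiple imputation will be used to handle missing data at week 24". It then describes the procedure for FVC, SpO2 and PedsQL only. From week 52 on it restricts the analysis to observed values. Protocol 2.1.3 says that week 52 will not be available for every patient.

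**The concern.** The protocol treats patients with open physes as the group to be followed for growth-plate change; the SAP percentage, by default, does not. At least 20 of at least 30 patients are to be adolescents aged 12 to 17, and the protocol itself provides for closed physes, so the base may well include patients who were never re-imaged.

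Effects on bone development are a named paediatric risk in Protocol 1.4.2, and this secondary endpoint quantifies them. The trial has no hypothesis tests, so the displayed N (%) is the result. With few or no findings, the reader's reassurance comes from the N. Counting patients who could not show a finding can only lower the percentage and tighten what seems to be ruled out.

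At week 52 the base could be all treated patients or only those with observed values. A literal observed-values rule also fits poorly with a cumulative count, because it could drop an early finding in a patient who has no week-52 read.

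**Working it through.** The plan states no figure for this endpoint, so there is none to reproduce.

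**Inputs from the documents.** About 20 nintedanib and 10 placebo patients (Protocol synopsis, 2:1 of 30); follow-up imaging in open physes only; base and case definition as above.

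**Assumed.** The number with open physes at baseline, m, which is not in the documents. It is shown from 20 of 20 (no effect) down to 12 of 20. The count of three findings is also illustrative.

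**Dilution.** With x findings, reported % = x/20 = (x/m) × (m/20), that is, the open-physes percentage times the open share.

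**Zero findings.** The exact (Clopper-Pearson) upper 95% limit is 1 − 0.025^(1/n).

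| Open physes, m | Open share | 3 findings, x/m | 0 findings, upper limit |
|---|---|---|---|
| 20 (same as all-TS) | 100% | 3/20 = 15.0% | 16.8% |
| 18 | 90% | 3/18 = 16.7% | 18.5% |
| 16 | 80% | 3/16 = 18.8% | 20.6% |
| 14 | 70% | 3/14 = 21.4% | 23.2% |
| 12 | 60% | 3/12 = 25.0% | 26.5% |

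The first row is what the all-TS base reports whatever the true m. The table assumes that every open-physes patient has a follow-up read. No interval is visibly planned for this table; the limits show what a reader can infer from the N.

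**Week 52: why the choice of base matters.** Take 20 treated, 12 open, three findings, half of the patients followed to week 52, and all three findings among those followed (all assumed):
- all treated (SAP 7 default): 3/20 = 15.0%
- treated and followed to week 52: 3/10 = 30.0%
- open physes at baseline: 3/12 = 25.0%
- open physes and followed to week 52: 3/6 = 50.0%

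**How many reach week 52 by the first database lock.** Protocol 3.2 assumes 18 months of recruitment (78 weeks) and a 26-week minimum. Follow-up is then 26 + (78 − entry week), so 52 weeks requires entry by week 52 of 78. Uniform entry (assumed) gives 52/78 = 0.667, or 20 of 30. Entry density rising linearly gives (52/78)² = 0.444, or 13; falling linearly, 1 − (26/78)² = 0.889, or 27. So about 10 of 30 (3 to 17) would lack week-52 follow-up at that lock.

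**Arm comparison.** Randomisation is stratified by age group, not physeal status (Protocol 4.1.3). Assume 21 adolescents split 14:7 and closed physes only among them, with 3 to 12 closed in total. The open shares of the two arms then differ on average by 0.082 to 0.136. At an equal assumed incidence of 25%, the average false difference is 0.25 × 0.082 = 0.021 to 0.25 × 0.136 = 0.034, about 2 to 3 points.

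**The case against.** The strongest reply is that the all-treated base is only a default. SAP 6.3 notes that numbers with available data may differ and points to section 6.6. There, the observed-values rule in 6.6.2.3 could override the default at week 52 and remove unimaged patients from the base. This stands: the dilution can be asserted under the visible rules for week 24 only, and week 52 is an ambiguity.

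Second, SAP 7 displays a missing category when values are missing, so the table may show how many patients were unimaged. This stands in part. The SAP does not say whether a patient with closed physes is coded as missing or as having no finding. Even if shown, the category leaves the percentage base unchanged and does not separate patients never scheduled for imaging from missed scans.

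Third, parts of the SAP are redacted and may hold an open-physes display. That cannot be excluded.

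Fourth, the endpoint is descriptive. Bone findings are also adverse events of special interest, enter the adverse-event tables with rates per 100 patient-years, and go to the Safety Monitoring Committee. So a reader should not infer that cases would be lost. Those routes capture the numerator; the exposure-adjusted rates address unequal follow-up but not physeal status.

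Two further inferences are tempting and not supported. One is that imaging findings will be multiply imputed at week 24: the opening sentence of 6.6.2.3 is broad, but the procedure covers only FVC, SpO2 and PedsQL, and the imaging subsection (6.6.2.4) has no imputation rule. The other is that the arm comparison is materially biased: the expected distortion is small.

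**Conclusion.** The point holds for week 24 under the visible default. If any treated patient has closed physes at baseline, the percentage understates the frequency among patients who could be assessed, by the factor of the open share. The direction is certain in that case; the size is not, because the share is unknown and the range starts at no effect. An unscheduled image could in principle show a finding in a patient with closed physes, but none is planned.

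For week 52 the documents support only the statement that the base of a cumulative count is not determined. They do not support saying that all treated patients will be used there.

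No test, error rate, power or patient management is affected. The imputation wording and the arm imbalance are minor and do not carry the point. It is a cheap improvement worth making to a named paediatric safety result.

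**What to change.** In SAP 5.2.2.1 and 7.5.2.3, keep the all-TS percentage and add beside it N (%) among TS patients with open physes at baseline and at least one post-baseline bone read by the time point. Show per arm the number with closed physes at baseline and the number with open physes but no post-baseline read, so that patients who left before any follow-up image stay visible.

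For week 52, use the same set and state how many were followed to week 52. A growth-plate change seen before week 52 is then kept, and patients without a finding are not dropped merely for lacking a week-52 read, so the base is not selected on having had a finding. Patients whose physes close during the trial remain in the set if they had a post-baseline read. One sentence should say that the multiple imputation in 6.6.2.3 does not apply to imaging findings.

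The cost is SAP wording and an extra table line: physeal status already decides who is imaged, and the reads are collected. The downside is smaller denominators and wider intervals.

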4. TREATMENTS

4.1 INVESTIGATIONAL TREATMENTS

The investigational medicinal products are nintedanib soft capsules 150 mg, 100 mg, 25 mg, and matching placebo capsules.

Nintedanib soft capsules 100 mg (oblong shape, 6.2 mm diameter and 16.3 mm length) and 150 mg (oblong shape, 7.1 mm diameter and 17.6 mm length) are commercially available for adults. Nintedanib soft capsules 25 mg of smaller size (oval shape, 5.1 mm diameter and 8.0 mm length) have been developed for this trial in the paediatric population. The 75 mg and 50 mg doses will be provided as multiples of the newly developed 25 mg dosage strength.

The sizes of the commercially available 100 mg and 150 mg capsules are considered suitable for the targeted age-range. However, for patients who are unable to swallow the commercially available form, a multiple of the 25 mg capsule is proposed as an alternative administration strategy for the 100 mg or 150 mg:

- 4 x 25 mg for the 100 mg
- 6 x 25 mg for the 150 mg

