Based on the assigned dose, including possible dose reduction, the daily dose of trial medication will consist of 1 capsule (150 mg, 100 mg, or 25 mg strength) or 2 capsules (25 mg strength), or 3 capsules (25 mg strength) to be taken per os twice daily (b.i.d.) (see [Table 4.1.2: 1](#)). Patients not able to swallow the 150 mg strength or the 100 mg strength capsule will have the possibility to take the 25 mg strength capsules (6 or 4 capsules per dose, respectively). To obtain kits with smaller capsules, an unscheduled visit should be registered in IRT. Once smaller capsules have been assigned, IRT will not allow to switch back to bigger capsules.

The patient should take the capsules twice daily, at about the same time every day (between 06:00 and 11:00 in the morning, 18:00 and 23:00 in the evening), with a dose interval of approximately 12 hours from one dose to the next dose.

The patient should swallow the whole capsules with water (a glass, approximately 250 mL) and should not chew or crush the capsules. If contact with the content of the capsule occurs, hands should be washed immediately and thoroughly. As nintedanib may cause stomach discomfort, the patient is recommended to take the capsules with food, i.e. during or immediately before or after a meal.

In case a dose is forgotten, the dose should be skipped if the time window to the next dose is less than 8 hours. The following dose should be taken according to the protocol. No catch up of missed doses is permitted.

In case of adverse events requiring a dose reduction between planned visits (see [Section 4.1.2](#) for details), the patient will attend an unscheduled visit. The investigator will visit the patient, record the reason for dose change, assign the new dose and instruct the patient and parent(s)/legal guardian on the number of capsules to be taken in the morning and in the evening until the next visit. Drug accountability will be completed carefully. Please refer to [Section 6.2.2](#) for instructions.

In case of adverse events requiring a dose interruption please refer to Section 4.1.2 for instructions.

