10.8 ACCEPTABILITY QUESTIONNAIRES

The assessment of acceptability of the investigational product based on the size and number of capsules will be performed by the patient using the acceptability questionnaire for the patient. If the patient is considered not old enough per investigator judgment, the parent/caregiver can assist with completion of the questionnaire.

Section to be completed before administration of the questionnaire

PATIENT NO.:

DATE OF COMPLETION: DD-MMM-YYYY

SIZE OF CAPSULES TAKEN DAILY: 150 MG, OR 100 MG, OR 25 MG

For 25 MG capsules ONLY

NUMBER OF CAPSULES TAKEN: IN THE MORNING _____

NUMBER OF CAPSULES TAKEN: IN THE EVENING _____

Acceptability questionnaire for the patient

We would like to learn about your impression of the study capsules.
Please take some time to answer the following questions.

For each question, please choose only the best applicable response.

QUESTION 1: HOW DOES IT FEEL WHEN YOU TAKE CAPSULES?

Very bad Bad Ok Good Very good

QUESTION 2: WAS TAKING THE STUDY CAPSULES (CHOOSE ONE OPTION):

- Very easy
- Easy
- Neither easy nor difficult
- Somewhat difficult
- Very difficult

QUESTION 3: HOW IS THE SIZE OF THE CAPSULE?

- OK (= acceptable)
- Large
- Very large

QUESTION 4: HOW EASY WAS TO SWALLOW THE GIVEN NUMBER OF CAPSULES? (CAPSULES SHOULD BE TAKEN WITH A GLASS OF WATER)

- I had no problem swallowing them (= acceptable)
- I swallowed them, but it was difficult
- I couldn't swallow them sometimes

QUESTION 5: COULD YOU TAKE THIS MEDICATION FOR A LONGER TIME PERIOD?

- yes
- no

Treatment acceptability questionnaire for the investigator or investigational site staff

Instructions:

For each question, please choose the response that most closely corresponds to this patient at the given time-point. Please consult the patient and his/her parents/caregiver if needed to answer the following questions:

QUESTION 1: WHAT IS YOUR IMPRESSION ABOUT THE PATIENT'S ACCEPTABILITY OF STUDY MEDICATION INTAKE? (CHOOSE ONE OPTION)

- Good
- Satisfactory
- Mediocre
- Bad
- Not assessable

QUESTION 2: STUDY MEDICATION INTAKE WAS POSSIBLE (CHOOSE ONE OPTION):

- Possible all the time
- Very often possible
- Occasionally not possible
- Often not possible
- Not assessable

**QUESTION 3: IF THE DRUG WAS NOT TAKEN, WAS THIS DUE TO:
(CHECK ALL ANSWERS THAT YOU CONSIDER APPLICABLE FOR THIS PATIENT AT THIS POINT IN TIME)**

- Lack of general well-being
- Difficulties to swallow the medication because of the capsule size

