Items are reverse-scored and linearly transformed to a 0-100 scale (0 = 100, 1 = 75, 2 = 50, 3 = 25, 4 = 0), so that higher scores indicate better health-related quality of life (HrQoL).

The specific instructions for deriving the PedsQL™ total score are provided in [Appendix Section 9.1](#).

5.2.2.7 Change in oxygen saturation (SpO₂) on room air at rest from baseline at week 24, and week 52

Oxygen saturation on room air at rest will be analysed.

5.2.2.8 Change in 6-min walk distance from baseline at week 24, and week 52

The exercise capacity of the patient will be recorded as distance covered in 6 minutes on the respective eCRF page. Furthermore, continuous pulse oximetry (SpO₂) will be performed and additional measurements such as pulse rate and blood pressure conducted.

The 6-minute walk test evaluation will primarily focus on the absolute change from baseline in the distance walked. Oxygen saturation measured by SpO₂, vital signs and BORG CR-10 Scales of the patient will be presented as scatterplots (each parameter versus age).

Only one value per period (pre-test, during test, post-test and recovery) patient, parameter and visit will be shown: for pulse rate, blood pressure and BORG scales the highest; for oxygen saturation and walking time the lowest value.

For more details please refer to CTP Section 5.1.6.

5.2.2.9 Patient acceptability based on the size of capsules at week 24

The acceptability questionnaire will be filled in by the patient. Further, to collect the investigator / site staff impression about the patient's acceptability of the study medication intake, the treatment acceptability questionnaire for the investigator or investigational site staff will be completed by the investigator / site staff.

The answer to question 3 on the patient's questionnaire "How is the size of the capsule" of the "Acceptability Questionnaire for the patient" will be used with categories "OK (=acceptable)", "Large", "Very large".

On the investigator questionnaire, the question 3 "If the drug was not taken, was this due to (check all answers that you consider applicable for this patient at this point in time" and others will be assessed to retrieve more information on the acceptability and palatability of the capsules.

An analysis of patients not taking the 100 mg b.i.d. or 150 mg b.i.d. form, i.e. who take 4x25 mg b.i.d. or 6x25 mg b.i.d., will be conducted in order to examine the swallowability.

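### Apart from one analysis of children on 4x25 or 6x25 mg, the visible SAP tabulates capsule-size and capsule-number acceptability only by arm and total, not by the capsules taken

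*SAP*

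**What the plan says.** SAP 5.2.2.9 and 5.2.2.10 define the two week-24 endpoints as the patient's answers to question 3 (size of the capsule) and question 4 (ease of swallowing the number given). For categorical endpoints, SAP 7.5.2.3 says: "Only descriptive analyses in the form of frequency tables will be performed". The layout of those tables comes from SAP section 7. Where nothing else is specified, "all analyses will be provided by randomized treatment group (placebo or nintedanib) and overall (total").

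SAP 5.2.2.9 adds one breakdown: "An analysis of patients not taking the 100 mg b.i.d. or 150 mg b.i.d. form", meaning those who take 4x25 or 6x25 mg twice daily instead. It also draws on the investigator questionnaire, including its item on why drug was not taken.

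Protocol 4.1 gives the capsule dimensions, states that placebo matches each strength, and explains where the small capsule comes from: "Nintedanib soft capsules 25 mg of smaller size (oval shape, 5.1 mm diameter and 8.0 mm length) have been developed for this trial". Under Protocol 4.1.4, a child who cannot swallow the 100 or 150 mg capsule may move to 25 mg capsules, and the move is one-way: "Once smaller capsules have been assigned, IRT will not allow to switch back to bigger capsules".

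The questionnaire header in Protocol Appendix 10.8 records the capsule strength and, for 25 mg users, the count: "NUMBER OF CAPSULES TAKEN: IN THE MORNING", with a second line for the evening.

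**The concern.** A child answers questions 3 and 4 about the capsules that he or she is taking. Those differ about twofold in length and from one to six in number, and the randomised arm does not determine them. A percentage by arm, or in total, therefore averages over very different things to swallow, with weights set by who happened to enrol. It cannot tell a reader whether the new 25 mg capsule is acceptable, or whether taking two or three of them per dose is.

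That matters because these are stated secondary endpoints and the small capsule is new. Most children under 10 are expected in weight bins 1 and 2 (Protocol 4.1.2), where the assigned regimens are 2x25 and 3x25 mg. The one planned breakdown does not reach those regimens.

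**Working it through.** The plan states no precision, power or target for acceptability, so there is no planned figure to reproduce. The check sets the capsule forms against the planned table dimensions, then shows how a pooled figure behaves.

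**1. What a child may take per dose** (Protocol 4.1, Table 4.1.2:1 and 4.1.4)

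| Form | Capsule length x diameter | When | Breakdown visible in the SAP |
|---|---|---|---|
| 1x150 mg | 17.6 x 7.1 mm | bin 4 | none |
| 1x100 mg | 16.3 x 6.2 mm | bin 3, or bin 4 reduced | none |
| 6x25 mg | 8.0 x 5.1 mm | bin 4, cannot swallow the large capsule | yes (5.2.2.9) |
| 4x25 mg | 8.0 x 5.1 mm | bin 3 or bin 4 reduced, cannot swallow the large capsule | yes (5.2.2.9) |
| 3x25 mg | 8.0 x 5.1 mm | bin 2, or bin 3 reduced | none |
| 2x25 mg | 8.0 x 5.1 mm | bin 1, or bin 2 reduced | none |
| 1x25 mg | 8.0 x 5.1 mm | bin 1 reduced | none |

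This gives three sizes, five counts (1, 2, 3, 4, 6) and seven forms. The longest capsule is 17.6 / 8.0 = 2.2 times the shortest. Arm is not among the determinants. Randomisation is stratified by age group only (Protocol 7.4), so the weight mix can also differ between arms of about 20 and 10.

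**2. Behaviour of the pooled figure.** Let w be the share of patients on 25 mg capsules, p the proportion of them who find the size acceptable, and q the proportion among 100 and 150 mg users. Then

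pooled = w x p + (1 - w) x q.

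The documents give neither p nor q. Two assumed pairs show the range:

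| Share on 25 mg (w) | p = 95%, q = 60% | p = 90%, q = 70% |
|---|---|---|
| 20% | 67.0% | 74.0% |
| 33% | 71.7% | 76.7% |
| 50% | 77.5% | 80.0% |
| 67% | 83.3% | 83.3% |

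For example, 0.20 x 0.95 + 0.80 x 0.60 = 0.67. With no change in how acceptable any capsule is, the result moves by 83.3 - 67.0 = 16.3 points in the first case and 83.3 - 74.0 = 9.3 points in the second. It never equals either underlying rate. The same formula applies to question 4, with one-capsule and several-capsule children as the two groups.

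**3. Is a finer table workable?** If 30 patients were spread evenly (an assumption):

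- by strength: 30 / 3 = 10 per row
- by count: 30 / 5 = 6 per row
- by form: 30 / 7 = 4.3 per row
- by form within arm: 20 / 7 = 2.9 and 10 / 7 = 1.4

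The exact 95% interval is 69.2% to 100% for 10 of 10 acceptable and 39.8% to 100% for 4 of 4. Tables by strength or by count with arms pooled are usable as description. A table by arm and form would be close to a listing.

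**The case against.** The strongest reply is that the visible text may be incomplete. The default layout applies only where nothing else is specified. Protocol 7.2.2 defers subgroup analyses to the SAP. In the public SAP, the entry for secondary endpoint analysis under section 4.1 has no content, and several section numbers are absent. A table by strength could sit in removed text. This stands, so the point is limited to what is visible.

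Second, a reader might infer that the results describe no actual dosage form at all. The documents do not support that. SAP 5.2.2.9 plans the 4x25 and 6x25 mg analysis and uses the investigator questionnaire, which lists capsule size as a possible reason for not taking the drug.

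Third, a reader might infer that large-capsule acceptability will be overstated, because a child who failed on the large capsule answers at week 24 about the small one. No planned table reports a large-capsule figure, so there is no such result to bias. If two of 30 children switched (an assumption) and both answered favourably, the pooled figure would shift by at most 2/30 = 6.7 points. The selection matters only once a table by strength exists.

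Fourth, arm is not wholly irrelevant. Nausea and vomiting are among the commonest reactions to nintedanib and could affect answers about swallowing. The tables by arm can stay, but they do not answer the question about dosage form.

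**Conclusion.** The point holds for the visible SAP. Apart from the 4x25 and 6x25 mg analysis, questions 3 and 4 are tabulated only by arm and total. Those percentages depend on the weight mix enrolled and do not show the acceptability of the 25 mg capsule, or of 2x25 and 3x25 mg. Under the two assumed pairs of rates, the dependence on mix is 9.3 to 16.3 points. That range illustrates the mechanism and does not predict the result. The conclusion itself needs no assumed rate. It follows from matched placebo, weight-based dosing and the table dimensions named.

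The consequence is limited. The endpoints are secondary and descriptive, and the PK and safety primary analyses and the sample size are untouched. A reader might go further and want every switch to 25 mg capsules scored as not acceptable among children first assigned a large capsule. The documents do not call for that. It would create a new composite endpoint, and children who leave the 100 mg capsule through dose reduction or weight change would stay in its denominator while answering about another capsule.

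**What to change.** In SAP 5.2.2.9, add a week-24 frequency table of question 3 by capsule strength taken (150, 100, 25 mg), arms pooled. In SAP 5.2.2.10, add the same for question 4 by capsules per dose (1, 2, 3, 4, 6). Strength and the 25 mg count come from the questionnaire header, and the count is one for the two larger strengths.

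Beside these tables, report how many children first assigned a 100 or 150 mg capsule were switched to 25 mg capsules for swallowing difficulty. Take this from the IRT registration of smaller capsules, kept apart from moves due to dose reduction or weight change. Week-24 answers on the large capsules can then be read with that selection in view. If removed SAP text already specifies such tables, a cross-reference is enough.

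The cost is two tables and one count from data already collected, with no change to conduct. The drawback is small cells, about 10 per strength and 6 per count if 30 patients spread evenly, and fewer where they do not. The results should be presented as description only.
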